3.1.1 Investigator assessment using RECIST 1.1

3.1.1.1 Target lesions

Measurable disease is defined as having at least one measurable lesion which is ≥ 10 mm in the longest diameter (LD) (except lymph nodes which must have short axis ≥ 15 mm) with CT or magnetic resonance imaging (MRI) and which is suitable for accurate repeated measurements.

A patient can have a maximum of 5 measurable lesions recorded at baseline with a maximum of 2 lesions per organ (representative of all lesions involved suitable for accurate repeated measurement) and these are referred to as TLs. If more than one baseline scan is recorded then measurements from the one that is closest to randomisation will be used to define the baseline sum of TLs. It may be the case that, on occasion, the largest lesion does not lend itself to reproducible measurement in which circumstance the next largest lesion, which can be measured reproducibly, should be selected.

All other lesions (or sites of disease) not recorded as TL should be identified as NTL at baseline. Measurements are not required for these lesions, but their status should be followed at subsequent visits.

If a patient has had a tumour assessment which cannot be evaluated then the patient will be assigned a visit response of not evaluable (NE) (unless there is evidence of progression in which case the response will be assigned as PD).

Please refer to CSP Appendix C for the definitions of complete response (CR), partial response (PR), stable disease (SD) and PD and the derivations of overall visit response using the information from target lesions (TL), non-target lesions (NTL) and new lesions.

Rounding of TL data

For calculation of PD and PR for TLs, percentage changes from baseline and previous minimum should be rounded to 1 decimal place before assigning a TL response. For example, 19.95% should be rounded to 20.0% but 19.94% should be rounded to 19.9%.

Missing TL data

For a visit to be evaluable, all TL measurements should be recorded. However, a visit response of PD should be assigned if any of the following occurred:

- A new lesion is recorded;
- A NTL visit response of PD is recorded;
- The sum of TLs is sufficiently increased to result in a 20% increase, and an absolute increase of ≥ 5 mm from nadir even assuming the non-recorded TLs have disappeared.

The nadir can only be taken from assessments where all the TLs had an LD recorded.

Lymph nodes

For lymph nodes, if the size reduces to < 10 mm, these are considered non-pathological.

However a size will still be given and this size should still be used to determine the TL visit response as normal. In the special case where all lymph nodes are < 10 mm and all other TLs are 0 mm, although the sum may be > 0 mm, the calculation of TL response should be overwritten as a CR.

TL visit responses subsequent to CR

A CR response can only be followed by CR, PD or NE. If a CR has occurred, the following rules at the subsequent visits must be applied:

- Step 1: If all lesions meet the CR criteria (i.e., 0 mm or < 10 mm for lymph nodes), the response will be set to CR irrespective of whether the criteria for PD or TL is also met (i.e., if a lymph node LD increases by 20% but remains < 10 mm).
- Step 2: If some lesion measurements are missing but all other lesions meet the CR criteria (i.e., 0 mm or < 10 mm for lymph nodes), the response will be set to NE irrespective of whether when referencing the sum of TL diameters the criteria for PD is also met.
- Step 3: If not all lesions meet the CR criteria, and the sum of lesions meets the criteria for PD, the response will be set to PD.
- Step 4: If, after steps 1 through 3, a response cannot be determined, the response will be set to remain as CR.

TL too big to measure

If a TL becomes too big to measure, this should be indicated in the database and a size ('x') above which it cannot be accurately measured should be recorded. If using a value of x in the calculation of TL response would not give an overall visit response of PD, then this will be flagged and reviewed by the study team blinded to treatment assignment. It is expected that a visit response of PD will remain in the vast majority of cases.

TL too small to measure

If a TL becomes too small to measure a value of 5 mm will be entered into the database and used in TL calculations, unless the radiologist has indicated and entered a smaller value that can be measured reliably. If a TL response of PD results then this will be reviewed by the study team blinded to treatment assignment.

Irradiated lesions/lesion intervention

Previously irradiated lesions (i.e., lesion irradiated prior to entry into the study) should be recorded as NTLs and should not form part of the TL assessment.

Any TL (including lymph nodes), which has had intervention during the study (for example, irradiation/palliative surgery/embolisation), should be handled in the following way:

- Step 1: the diameters of the TLs (including the lesions that have had intervention) will be summed and the calculation will be performed in the usual manner. If the visit response is PD this will remain as a valid response category.
- Step 2: If there was no evidence of progression after step 1, the lesion diameter (for those lesions with intervention) will be treated as missing and scaled up as described previously as long as there remain $\leq 1/3$ of the TLs with missing measurements. If the scaling results in a visit response of PD then the subject will be assigned a TL response of PD.
- Step 3: If after both steps PD has not been assigned, then a scaled sum of diameters will be calculated, treating the lesion with intervention as missing, and PR or SD then assigned as the visit response. Subjects with intervention are evaluable for CR as long as all non-intervened lesions are 0 (or < 10 mm for lymph nodes) and the lesions that have been subject to intervention also have a value of 0 recorded.

At subsequent visits the above steps will be repeated to determine the TL and overall visit response. When calculating the previous minimum, lesions with intervention should be treated as missing and scaled up (as per step 2 above).

Once a lesion has had intervention then it should be treated as having intervention for the remainder of the study noting that an intervention will most likely shrink the size of tumors.

Lesions that split in two

If a TL splits in two, then the LDs of the split lesions should be summed and reported as the LD for the lesion that split.

Lesions that merge

If two TLs merge, then the LD of the merged lesion should be recorded for one of the TL sizes and the other TL size should be recorded as 0mm.

Change in method of assessment of TLs

Computerized tomography (CT) scan and MRI are the only methods of assessment that can be used within this trial. If a change in method of assessment occurs between CT scan and MRI this will be considered acceptable and no adjustment within the programming is needed.

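### After a target-lesion CR, Step 4 scores an incomplete visit with sub-PD regrowth as CR, while the same visit without regrowth is NE

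*SAP*

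**What the plan says.** SAP section 3.1.1.1 contains a general rule for missing target lesions and a special rule for visits after a CR.

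- **General rule (Missing TL data).** "For a visit to be evaluable, all TL measurements should be recorded". PD can still be assigned from a new lesion, from non-target PD, or from the recorded TLs alone if they show a 20% rise and an "absolute increase of ≥ 5 mm from nadir even assuming the non-recorded TLs have disappeared". Earlier in the same section, an assessment that cannot be evaluated is NE unless there is evidence of progression.
- **Special rule (TL visit responses subsequent to CR).** The steps are mandatory, and the only responses open are CR, PD and NE. Step 1 gives CR when every lesion meets the CR criteria. Step 2 begins "Step 2: If some lesion measurements are missing but all other lesions meet the CR criteria" and gives NE. Step 3 gives PD when some lesion no longer qualifies and the sum reaches the PD threshold. The catch-all is "Step 4: If, after steps 1 through 3, a response cannot be determined, the response will be set to remain as CR".

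**The concern.** The special rule gives NE for missing data only when every recorded lesion still meets the CR criteria. Once a recorded lesion has regrown, Step 2 no longer applies. If the recorded sum is also below PD, Step 3 does not apply either, and Step 4 returns CR although a TL is missing. Of two equally incomplete visits, the one with worse findings gets the better response. The general rule would make both NE.

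The result feeds other derivations:

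- **Overall response (section 3.1.1.3, Table 2).** With no new lesion and no non-target PD, a TL response of NE gives overall NE. A TL response of CR gives overall CR or PR, depending on the non-target lesions.
- **Confirmed response (section 3.2.2).** A visit wrongly scored CR can be the one that confirms a response at least 4 weeks after it was first seen.
- **PFS and DoR (sections 3.2.1 and 3.2.3).** A CR visit is evaluable and an NE visit is not. The score can therefore move the censoring date and restart the count for two missed visits.

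**Working it through.** The plan gives no figure to reproduce, so the check traces its rules.

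**Inputs from SAP section 3.1.1.1**
- CR criterion: 0 mm for a non-nodal TL, below 10 mm for a node.
- Nodes below 10 mm keep their measured size in the sum, so the nadir at CR can exceed 0 mm.
- PD on TLs: rise from nadir of at least 20% (rounded to one decimal) and at least 5 mm, with unrecorded TLs counted as 0 in the visit sum.

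**Assumptions.** The lesion sizes are illustrative. Each patient has two TLs, and the CR visit is the nadir. Any rise from a nadir of 0 mm is taken to meet the 20% limb.

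**Formulas.** Rise = recorded sum − nadir. Percentage = 100 × rise / nadir.

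| TLs at CR (nadir) | Later visit | Rise | Percentage | Result |
|---|---|---|---|---|
| Nodes 8 + 8 (16 mm) | 8, missing | – | – | NE, Step 2 |
| | 11, missing | 11 − 16 = −5 | – | CR, Step 4 |
| | 20, missing | 20 − 16 = 4 | 25.0% | CR, Step 4 (4 < 5 mm) |
| | 21, missing | 21 − 16 = 5 | 31.3% | PD, Step 3 |
| Node 8 + non-nodal 0 (8 mm) | 8, missing | – | – | NE, Step 2 |
| | missing, 5 | 5 − 8 = −3 | – | CR, Step 4 |
| | missing, 12 | 12 − 8 = 4 | 50.0% | CR, Step 4 |
| | missing, 13 | 13 − 8 = 5 | 62.5% | PD, Step 3 |
| Non-nodal 0 + 0 (0 mm) | 0, missing | – | – | NE, Step 2 |
| | 4, missing | 4 − 0 = 4 | limb taken as met | CR, Step 4 |
| | 5, missing | 5 − 0 = 5 | limb taken as met | PD, Step 3 |

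The gap is widest when nodes contribute to the nadir, because the missing node counts as 0 in the visit sum but stays in the nadir. In the first patient a 20 mm node is scored CR, although the section treats a node of 15 mm or more as measurable disease. In the second, a reappeared non-nodal lesion of up to 12 mm is scored CR, although 10 mm or more is measurable.

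With only non-nodal TLs the gap is narrow: a recorded size of 1 to 4 mm. A lesion too small to measure is entered as 5 mm unless a smaller reliable value is given, and from a nadir of 0 mm that already reaches PD, subject to the study team's review.

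Step 4 has a proper role when everything is recorded. Nodes of 11 and 8 mm against a nadir of 16 mm give a rise of 19 − 16 = 3 mm, which is not PD. PR and SD are barred after a CR, so CR is the section's convention there. That argument fails for incomplete visits, because NE is one of the permitted responses.

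**The case against.** The strongest reply is that the general evaluability rule governs, so a sensible programmer would return NE. The text does not secure this. The post-CR steps are the more specific rule, they are mandatory, and Step 4 is unconditional. Responses are derived by program from investigator data with no central review (section 3.1), so two programmers could defensibly differ.

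Several points on scale do stand. The TL response is overridden by non-target PD or a new lesion (Table 2). Group A has no tumour scans after protocol version 2.0. Reporting is descriptive, with no hypothesis testing (section 4).

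A reader might also infer more than the document supports:

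- **That clear regrowth from a nadir of 0 mm is scored CR because the percentage is undefined.** The PD wording asks for a sum increased enough to be 20% and 5 mm above nadir. Read as a threshold, a rise from 0 to 20 mm meets both limbs. The adverse result needs a particular coding error, and the PD definitions are referred to a protocol appendix that is not at hand.
- **That a visit with no TL measured is certainly CR.** This is only ambiguous. Step 2 speaks of some lesions missing, so a literal reading falls through to Step 4. Step 2 can also be read as met when nothing is recorded, and the general NE rule points the same way.
- **That progression events are lost.** The affected visits are below the SAP's PD threshold by construction, and the fix would make them NE, not PD.
- **That every error lengthens response or PFS.** Scoring CR rather than NE restarts the missed-visit count, so a later progression or death may be counted as an event instead of being censored early. That can lower the Kaplan-Meier estimate.
- **That ORR shifts by about 7 points.** One patient is 1/15 = 6.7% to 1/14 = 7.1% of an arm, if 29 patients split 14 and 15 (an assumption). It affects confirmed ORR only, and only if no other visit confirms the response.

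**Conclusion.** The rule is wrong as written for one defined class of visit: after a TL CR, at least one TL missing, a recorded TL no longer at CR, and a recorded sum below PD. Step 4 returns CR where the section's general rule and the logic of Step 2 call for NE.

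The consequence is probably small. It needs an earlier TL CR among 29 randomised patients and then an incomplete visit with sub-PD regrowth. Confirmed response changes only if that visit is the sole confirmation. The censoring date moves only if the patient is later censored with no later evaluable scan. The direction of any effect on PFS can vary. The sizes in the table are illustrative, and how many patients would be affected cannot be known from the SAP. This is a minor correction, worth making because the text is mandatory and would be programmed.

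**What to change.** In SAP section 3.1.1.1, under TL visit responses subsequent to CR:

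1. Insert before Step 4: *If any or all TL measurements are missing and PD is not shown under Step 3, the TL response is NE.*
2. Limit Step 4 to visits at which all TLs are recorded.

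The inserted sentence also settles the visit with no TL measured. PD visits and fully recorded visits with sub-PD regrowth keep their present result. No added wording for a nadir of 0 mm is needed for this point.

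The cost is one sentence, one qualifier and a small program change. The downside is that an occasional post-CR visit becomes NE, which the general rule already calls for.

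### For target lesions treated on study, the one-third limit governs PD from the scaled sum (Step 2) but not PR or SD (Step 3), and the scaling is not defined in the SAP

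*SAP*

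**What the plan says.** SAP section 3.1.1.1, under the paragraph on irradiated lesions and lesion intervention, sets three steps for a TL treated during the study.

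- Step 1 sums all TLs, treated ones included, and keeps PD if that sum shows it.
- Step 2 applies if Step 1 shows no progression. The treated lesion is "treated as missing and scaled up as described previously as long as there remain" no more than one third of TLs missing. Then: "If the scaling results in a visit response of PD then the subject will be assigned a TL response of PD".
- Step 3 opens with "If after both steps PD has not been assigned" and continues: "then a scaled sum of diameters will be calculated, treating the lesion with intervention as missing, and PR or SD then assigned as the visit" outcome. No limit on the share of treated TLs is stated, and neither NE nor PD is among the outcomes. CR has its own condition.

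The steps are repeated at later visits, and treated lesions are also scaled when the previous minimum is calculated, by reference to Step 2.

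The only rule on missing TLs that stands before this is in the same section, under missing TL data. It contains no scaling: "For a visit to be evaluable, all TL measurements should be recorded". PD is still assigned if the recorded lesions reach the threshold with the unrecorded ones counted as gone, and "The nadir can only be taken from assessments where all the TLs had an LD recorded".

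**The concern.** The two steps use the same scaled sum but different entry conditions. Above one third treated, the sum is considered too incomplete to show progression, yet it may still show response or stability. The SAP itself expects an intervention to shrink a lesion, so the raw sum in Step 1 is a weak safeguard in exactly these patients.

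The reference to scaling described previously leads to nothing in the SAP. Visit responses are derived by program (section 3.1), so the programmer would have to choose a formula.

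The TL response feeds the investigator-assessed outcomes. PFS counts progression regardless of other anti-cancer therapy (section 3.2.1), so a progression not recognised at a visit delays the event. An SD that should have been NE also moves the censoring date, which is the last evaluable assessment. Duration of response follows the PFS dates (3.2.3). Best overall response and disease control rate use the visit responses (3.2.4, 3.2.5), and dose intensity uses the progression date (3.3.8).

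**Working it through.** The SAP gives no figure on this point to reproduce, so the check applies the three steps literally to worked cases.

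**Inputs from the SAP.** 1 to 5 TLs; PD is an increase of at least 20% and at least 5 mm over the nadir; Step 2 is limited to one third missing (all section 3.1.1.1). 29 patients were randomised, with 1:1 allocation (section 1.3).

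**Assumptions.** The SAP gives no formula, so proportional scaling is assumed: scaled sum = current sum of untreated TLs × (baseline sum of all TLs / baseline sum of untreated TLs). PR is taken as at least 30% below baseline, the usual RECIST 1.1 threshold, which the SAP leaves to Appendix C of the protocol. Lesion sizes are illustrative.

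**When Step 2 is barred (treated / total > 1/3).**
- 1 TL: any intervention (1/1). No untreated lesion remains, so the denominator of the scaling is zero and the scaled sum does not exist.
- 2 TLs: any intervention (1/2 or 2/2).
- 3, 4 or 5 TLs: two or more treated (2/3, 2/4, 2/5 and above).

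**Case A: 2 TLs, baseline and nadir 30 + 30 = 60 mm, now 45 mm untreated and 5 mm treated.**
- Step 1: 45 + 5 = 50 mm; (50 − 60)/60 = −16.7%. No PD.
- Step 2: 1/2 > 1/3, barred.
- Scaled sum: 45 × 60/30 = 90 mm; +50.0% and +30 mm over nadir. This meets PD.
- Step 3: only PR or SD is available, so SD.

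**Case B: 3 TLs, baseline and nadir 3 × 30 = 90 mm, two treated, now 40 mm untreated, 10 and 10 mm treated.**
- Step 1: 60 mm; −33.3%. No PD.
- Step 2: 2/3 > 1/3, barred.
- Scaled sum: 40 × 90/30 = 120 mm; +33.3% and +30 mm. This meets PD.
- Step 3: SD.

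**Case C: 2 TLs, baseline 60 mm, nadir 15 + 15 = 30 mm, now 20 mm untreated and 5 mm treated.**
- Step 1: 25 mm; −16.7% against nadir. No PD.
- Step 2: barred (1/2).
- Scaled sum: 20 × 60/30 = 40 mm; +33.3% and +10 mm over nadir, which meets PD; (40 − 60)/60 = −33.3% against baseline.
- Step 3: PR.

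**Control: 3 TLs, baseline and nadir 90 mm, one treated, now 40 + 40 mm untreated and 10 mm treated.**
- Step 1: 90 mm; 0%. No PD.
- Step 2: 1/3 is within the limit. Scaled sum 80 × 90/60 = 120 mm; +33.3% and +30 mm, so PD is assigned.

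At or below one third the steps therefore work as intended; the fault appears only above it.

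**Size per patient.** With 14 or 15 patients per arm, one patient is 1/14 = 7.1 or 1/15 = 6.7 percentage points of an arm's rate. This is an upper bound, reached only if the affected visit changes that patient's best response.

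**The case against.** **Step 3 may inherit the limit.** Step 3 could be read as reusing the sum from Step 2 with its limit, and section 3.1.1.1 has a general default of NE for an assessment that cannot be evaluated. That would be a sensible rule, and it would also cover the single treated TL. It is not what the text says: Step 3 is triggered simply by the absence of PD, calculates its own scaled sum, and names only PR or SD.

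**The protocol may define the scaling.** Its Appendix C is not at hand. The SAP cites that appendix for response definitions and overall visit response, whereas the scaling reference points back within the SAP.

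**Masking is conditional.** A reader might infer that progression is generally hidden after local treatment. The SAP does not support this. PD on the raw sum is kept, Step 2 catches PD at or below one third, and a new lesion or non-target progression gives overall PD regardless. This part of the objection stands.

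**No clear conflict with the missing-data rule.** A reader might also infer that the evaluability and nadir rules contradict the intervention rule. They concern lesions with no recorded measurement. A treated lesion normally still has a recorded diameter, which Step 1 uses, and is only handled as missing in one calculation. This too stands; at most a clarification is needed.

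**Response is not inflated against the recorded sizes.** In Case C the raw sum is 25 mm, or (25 − 60)/60 = −58.3% from baseline, so the scaled −33.3% is the more cautious figure. An increase in ORR can be claimed only relative to NE. ORR and best response are also less exposed if the intervention counts as subsequent anti-cancer therapy (sections 3.2.2 and 3.2.5).

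**Practical weight is low.** Efficacy is exploratory, there is no hypothesis testing, radiotherapy on study treatment is an example of an important deviation (section 2.2), and Group A has no tumour scans after protocol version 2.0.

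**Conclusion.** The point holds as a minor defect. The one-third limit is attached to Step 2 only, and the scaling it relies on is not described in the SAP. When more than one third of TLs have been treated, the raw sum is short of PD, and there is no new lesion or non-target progression, a scaled sum that meets PD can be recorded as SD or PR. With one TL, treated, PR or SD is required from a sum that cannot be calculated.

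The worked cases rest on proportional scaling and a 30% PR threshold. The asymmetry between the steps and the missing formula rest on the SAP text alone. How many patients meet the conditions is not stated, so no bias in the reported PFS or response figures can be asserted. With only descriptive summaries of 29 patients, no decision rule depends on it.

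**What to change.** 1. Apply the one-third limit to Step 3. If it is exceeded and Step 1 shows no PD, set the TL response to NE, keeping the existing CR condition. New lesions and non-target progression continue to give overall PD.
2. State the scaling in the SAP, for example: sum of untreated TLs × (baseline sum of all TLs / baseline sum of untreated TLs). Say that the same limit applies when the previous minimum is scaled.
3. Optionally, add a sentence to the missing-data paragraph that treated lesions with a recorded diameter follow the intervention rule.

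A separate exception for untreated TLs that meet PD by themselves is largely redundant: the raw sum is at least as large as the untreated sum, so against the same nadir Step 1 would already give PD.

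The cost is a few sentences and a small change to the RECIST program. A few visits become NE instead of SD or PR. In Cases A to C the result would be NE, not PD, so the change removes unsupported SD and PR calls without itself adding progression events. Cases at or below one third, such as the control, do not change.

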3.1.1.2 NTLs and new lesions

At each visit an overall assessment of the NTL response should be recorded by the investigator. This section provides the definitions of the criteria used to determine and record overall response for NTL at the investigational site at each visit.

Please refer to CSP Appendix C for the definitions of CR, PR, SD and PD and the derivations of overall visit response using the information from target lesions (TL), non-target lesions (NTL) and new lesions.

To achieve ‘unequivocal progression’ on the basis of NTLs, there must be an overall level of substantial worsening in non-target disease such that, even in the presence of SD or PR in TLs, the overall tumour burden has increased sufficiently to merit a discontinuation of therapy. A modest ‘increase’ in the size of one or more NTLs is usually not sufficient to qualify for unequivocal progression status.

Details of any new lesions will also be recorded with the date of assessment. The presence of one or more new lesions is assessed as progression.

A lesion identified at a follow up assessment in an anatomical location that was not scanned at baseline is considered a new lesion and will indicate disease progression.

The finding of a new lesion should be unequivocal: i.e. not attributable to differences in scanning technique, change in imaging modality or findings thought to represent something other than tumour.

New lesions will be identified via a Yes/No tick box. The absence and presence of new lesions at each visit should be listed alongside the TL and NTL visit responses.

A new lesion indicates progression so the overall visit response will be PD irrespective of the TL and NTL response.

If the question ‘Any new lesions since baseline’ has not been answered with Yes or No and the new lesion details are blank this is not evidence that no new lesions are present and should be treated as NE in the derivation of overall visit response.

Symptomatic deterioration is not a descriptor for progression of NTLs: it is a reason for stopping study therapy and will not be included in any assessment of NTLs.

Patients with ‘symptomatic deterioration’ requiring discontinuation of treatment without objective evidence of disease progression at that time should continue to undergo RECIST 1.1 tumour assessments where possible until objective disease progression is observed.

